#### **11.10.2. 6-Month Follow-up (90 days following the 3-month visit date $\pm$ 30 days)**

All enrolled subjects must be evaluated approximately 6 months after the index procedure (3 months after the 3-month visit). The follow-up assessment may be performed via telephone interview with the subject or during an office visit. During the 6-month follow-up, the following assessments must be completed.

- AE assessment and source document collection as described in Section 20.
- Documentation of current antiplatelet medications (P2Y12 inhibitor and aspirin). Information pertaining to dose changes, medication interruptions (3 days or greater), and medication cessation must be documented.

#### **11.10.3. 12-Month Follow-up (270 days following the 3-month visit date $\pm$ 30 days)**

All enrolled subjects must be evaluated approximately 12 months after the index procedure (9 months after the 3-month visit). The follow-up assessment may be performed via telephone interview with the subject or during an office visit. During the 12-month follow-up, the following assessments must be completed.

- AE assessment and source document collection as described in Section 20.
- Documentation of current antiplatelet medications (P2Y12 inhibitor and aspirin). Information pertaining to dose changes, medication interruptions (3 days or greater), and medication cessation must be documented.

#### **11.10.4. 15-Month Follow-up (365 days following the 3-month visit date\* + 30 days)**

All enrolled subjects must be evaluated approximately 15 months after the index procedure (12-months after the 3-month visit). The follow-up assessment may be performed via telephone interview with the subject or during an office visit. During the 15-month follow-up, the following assessments must be completed.

- AE assessment and source document collection as described in Section 20.
- Documentation of current antiplatelet medications (P2Y12 inhibitor and aspirin). Information pertaining to dose changes, medication interruptions (3 days or greater), and medication cessation must be documented.

**11.10.5. Procedure for Determining When a Subject is Lost to Follow-Up**

A subject will not be considered lost to follow-up unless the subject misses the 15-month follow-up visit. A minimum of 3 attempts (i.e., 2 phone calls followed by a certified letter) should be made to contact the subject for each missed follow-up visit. This information should be documented in the source.

## 12. Statistical Considerations

### 12.1. Endpoints

#### 12.1.1. Co-Primary Endpoints

There are two powered co-primary endpoints:

1. The rate of death or myocardial infarction (MI) between 3 and 15 months expressed as the proportion of subjects who experience death/MI between 3 and 15 months among all subjects who either experience death/MI between 3 and 15 months or survive free of death/MI for at least 425 days.
2. The rate of Academic Research Consortium (ARC) definite/probable stent thrombosis (ST) involving SYNERGY between 3 and 15 months expressed as the proportion of subjects who experience ARC ST between 3 and 15 months among all subjects who either experience ARC ST between 3 and 15 months or survive free of ARC ST for at least 425 days.

##### 12.1.1.1. Hypotheses

###### Death/MI:

The null hypothesis that the difference of death/MI rates between SYNERGY with 3-month DAPT (test group) and historical DES with 12-month DAPT (control group) is greater than or equal to the non-inferiority margin will be tested against the alternative hypothesis that the difference between test group and control group is less than the non-inferiority margin in subjects at high risk for bleeding:

$$H_0: P_{\text{Death/MI-3M}} - P_{\text{Death/MI-12M}} \geq \Delta$$

$$H_1: P_{\text{Death/MI-3M}} - P_{\text{Death/MI-12M}} < \Delta$$

where  $P_{\text{Death/MI-3M}}$  and  $P_{\text{Death/MI-12M}}$  are the 3 to 15-month death/MI rates for the 3-month DAPT test group and 12-month DAPT group (historical control), respectively, and  $\Delta$  is the non-inferiority margin.

A propensity score model using quintile adjustment for death/MI will be used to test the hypothesis of non-inferiority of the test group compared to historical control group.

###### ARC-defined ST:

The null hypothesis that ARC ST rate is greater than or equal to the performance goal will be tested against the alternative hypothesis that ARC ST rate for the is less than the performance goal:

$$H_0: P_{\text{ST-3M}} \geq \text{PG}$$

$$H_1: P_{\text{ST-3M}} < \text{PG}$$

where  $P_{ST-3M}$  is the rate of 3 to 15-month ARC-defined definite/probable ST involving SYNERGY for the 3-month DAPT group, and PG is the performance goal.

#### 12.1.1.2. Sample Size

##### Death/MI:

The expected rate of 5.6% for 3 to 15 month death/MI rates in subjects at high risk for bleeding for both test and control groups is estimated from BSC PROMUS subjects extracted from the HCRI DAPT, PE+ PAS, and PE PROVE studies. The non-inferiority margin is 2.52%, which is 45% of the expected rate. With one-sided 2.5% significance level, the study will require a minimum of 1,500 evaluable subjects per group to provide 85% power to reject the null hypothesis when the alternative hypothesis is true. With consideration of additional 10% subjects accounting for model variability, number of evaluable subjects in the test group required in the propensity score model is 1,650 (1,500 \* 1.1). In the control group, there are approximately 1,643 historical -limus DES high risk for bleeding subjects available from Boston Scientific sponsored trials (403) and the HCRI DAPT Study minus TAXUS (1,240). Assuming that the dropout rate due to the ineligibility between 0 and 3 months for 3-month DAPT test group is 15% and the expected attrition rate between 3 and 15 months is 3%, the study needs to enroll 2,000 subjects in the 3-month DAPT test group.

The enrollment may be terminated earlier if the observed dropout rate between 0 and 3 months is projected to be less than 15%. Enrollment may be continued beyond 2,000 subjects (up to a maximum of 2,250 subjects) if the observed dropout rate in 0 to 3 months is projected to be >15%.

The sample size calculation is based on 2-group test of equivalence in proportions with equal allocation using nQuery Advisor® Version 5.0

##### ARC-defined ST:

The expected rate of 3 to 15-month rate of ARC-defined definite/probable ST in subjects at high risk for the test group is less than 0.4% based on HCRI DAPT, PE+ PAS, and PE PROVE studies. The performance goal is set to be 1%. With a one-sided 2.5% significance level, 1,650 evaluable subjects will be required to provide 80% power to reject the null hypothesis when the alternative hypothesis is true. Assuming that the dropout rate due to the ineligibility between 0 and 3 months for the test group is 15% and the expected attrition rate between 3 and 15 months is 3%, the study needs to enroll 2,000 subjects for the test group.

The enrollment may be terminated earlier if the observed dropout rate between 0 and 3 months is projected to be less than 15%. Enrollment may be continued beyond 2,000 subjects (up to a maximum of 2,250 subjects) if the observed dropout rate in 0 to 3 months is projected to be >15%.

The sample size is calculated using an exact test for single proportion using nQuery Advisor® Version 5.0.

12.1.1.3. Statistical Methods

Death/MI:

A propensity score model with quintile adjustment will be used to address baseline imbalance between the test group and the historical control group. The null hypothesis will be tested against alternative hypothesis using the propensity score quintile adjusted death/MI co-primary endpoint for testing non-inferiority between the test group and the historical control group.

The propensity score will be estimated by using logistic regression with inclusion of all pre-specified baseline covariates in the model as the predictor variables and the treatment groups (test vs control) as the dependent variable.

The entire study analysis set will be divided into propensity score quintiles. The death/MI co-primary endpoints will be calculated by study group within each quintile. The adjusted measure for each study group is a simple mean of the five propensity score quintile estimates. Similarly, the stratified between-group difference estimate is the mean of the quintile difference estimates, and the adjusted standard error is obtained from the square root of the mean of the five quintile variances.

Let  $d_i, i = 1, \dots, 5$  be the quintile difference estimates,  $se_i, i = 1, \dots, 5$  are the standard errors of the quintile difference estimates, and  $var_i, i = 1, \dots, 5$  are the corresponding variances where  $var_i = se_i^2$ . The adjusted between-group difference estimate is  $\bar{d} = \frac{1}{5} \sum_{i=1}^5 (d_i)$ ,  $Var(\bar{d}) = \frac{1}{5^2} \sum_{i=1}^5 var(d_i)$ , and  $SE(\bar{d}) = \sqrt{Var(\bar{d})}$ .

The adjusted between-group difference estimate ( $\bar{d}$ ) and the standard error ( $SE(\bar{d})$ ) of the adjusted between-group difference will be used to construct the 97.5% upper confidence bound of the adjusted between-group difference using normal approximation to binomial (z-test). If the 97.5% upper confidence bound is less than the non-inferiority margin, the null hypothesis will be rejected for the death/MI co-primary endpoint and the test group will be concluded to be non-inferior to historical control group.

The covariates for propensity score model will include the following variables in different categories, which are available in both the short DAPT study and the historical control studies:

Table 12.1-1: Propensity Score Model Covariates

Category	Covariates
Geographic Location	region (US vs OUS)
Demographics	age, gender, race/ethnicity
Physical Assessment	height, weight
Medical History	smoking status, medically treated diabetic, hypertension requiring medication, hyperlipidemia requiring medication, history of CHF, history of MI, current angina status (stable/unstable/silent ischemia/none), history of PCI, history of CABG, LVEF, history of CVA, history of renal disease/insufficiency/failure, history of PVD, anticoagulant therapy, history of major bleeding
Target Lesion/ Pre-Procedure*	CASS site, lesion length (visual), RVD (visual), %DS (visual), calcification, tortuosity, per-procedure TIMI flow
Procedure/Post-Procedure	number of vessels treated (index + staged), number of lesions (index + staged), number of stents (index + staged), P2Y12 inhibitor type (0-3 months)
Additional angiographic data*	post-procedure TIMI flow, post-procedure %DS, dissection, perforation

\*For subjects with multiple lesions, the worst case of the multiple lesion characteristics will be used in the propensity score.

ARC-defined ST:

For the co-primary endpoint of ARC-defined (definite/probable) ST, the one-sided exact test for single proportion comparing the observed ARC ST rate of the test group to the pre-specified performance goal will be performed. Specifically, if the one-sided 97.5% upper confidence bound for the observed ARC ST rate of the test group is less than the performance goal, the test group will be considered to meet the performance goal.

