Co-Primary Endpoint (Death/MI) Sample Size Parameters	
 
• Expected 3 to 15 month death/MI rate in subjects at high risk for bleeding with 12-month DAPT (control) = 5.6%a
 
• Expected 3 to 15 month death /MI rate in subjects at high risk for bleeding with 3-month DAPT (test) = 5.6%a
 
• Non-inferiority margin = 2.52% (45% relative to the expected rate)
 
• Test significance level = 0.025 (1-sided)
 
• Power = 85%
 
• The unadjusted comparison requires a minimum of 1,500 evaluable subjects per group, which is based on equal allocation using 2-group test of equivalence in proportions in nQuery Advisor
 
• Control subjects are historical -limus DES subjects who were at high risk for bleeding extracted from Boston Scientific (BSC) sponsored trials PROMUS Element Plus US Post Approval Study (PE+PAS), PE PROVE European Post Approval Study, and the HCRI DAPT Study minus TAXUS subjects. The number of available historical control subjects is approximately 1,643 (403 from BSC + 1,240 from HCRI DAPT)
 
• Number of evaluable test subjects required in the propensity score model is 1,650 (1,500 * 1.1) including additional 10% subjects accounting for model variability
 
• Expected drop out rate due to ineligibility for 3 month DAPT in 0 to 3 months = 15%
 
• Expected attrition rate in 3 to 15 months = 3%
 

	
 
• N = 2,000b subjects enrolled
 
 
aThe expected rate of 5.6% for 3 to 15-month death/MI is estimated from BSC PROMUS subjects at high risk for bleeding extracted from the HCRI DAPT Study (13/253), PE+ US Post Approval Study (14/318), and PE PROVE European Post Approval Study (11/85).
 
bThe enrollment may be terminated early if the observed dropout rate in 0 to 3 months is projected to be <15%. Enrollment may be continued beyond 2,000 subjects (up to a maximum of 2,250 subjects) if the observed dropout rate in 0 to 3 months is projected to be >15%.

Co-Primary Endpoint (Stent Thrombosis) Statistical Hypothesis	Rate of Academic Research Consortium (ARC) definite/probable stent thrombosis (ST) involving SYNERGY between 3 and 15 months in subjects at high risk for bleeding is less than the performance goal (PG) of 1%

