## 12.2. *General Statistical Methods*

All statistical analyses will be performed using the SAS System software, version 9.3 or later (Copyright© 2002-2010 by SAS Institute Inc., Cary, North Carolina, USA. All rights reserved).

All statistical analyses will be conducted according to applicable Standard Operating Procedures, Work Instructions, and the study-specific Statistical Analysis Plan.

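### Section 12.1.1.3 states the adjusted standard error in words as √5 times the value in its own formula; the formula is right and the clause needs correcting

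*Combined protocol and SAP*

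**What the plan says.** The Death/MI part of section 12.1.1.3 defines the adjusted standard error twice.

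- **In words.** The estimate is a simple average across quintiles: "the stratified between-group difference estimate is the mean of the quintile difference estimates". The same sentence then says that "the adjusted standard error is obtained from the square root of the mean of the five quintile variances".
- **In symbols.** The next paragraph sets d̄ = (1/5) Σ d_i, Var(d̄) = (1/5²) Σ var(d_i), and SE(d̄) as the square root of Var(d̄).

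The decision rule refers to the symbols. The adjusted difference and the SE "of the adjusted between-group difference will be used to construct the 97.5% upper confidence bound of the adjusted between-group difference using normal approximation to binomial", and then: "If the 97.5% upper confidence bound is less than the non-inferiority margin, the null hypothesis will be rejected for the death/MI co-primary endpoint". Section 12.1.2.3 builds the bleeding bound from the same two symbols and compares it with zero.

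Section 12.2 adds that analyses will be "conducted according to applicable Standard Operating Procedures, Work Instructions, and the study-specific Statistical Analysis Plan".

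**The concern.** The two definitions sit in consecutive paragraphs and cannot both be right. The words divide the summed variance by 5 and the formula divides it by 25.

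The quantity sets the upper bound that decides non-inferiority for a co-primary endpoint, and the Synopsis makes study success depend on meeting both co-primary endpoints. The people who produce the result may also not be those who wrote the text. Section 12.2.2 passes the propensity models to a separate outcome reporting team, and section 12.2 points to a study-specific SAP. Someone who programs or validates from the sentence would not match a result built on the formula.

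**Working it through.** **Inputs**

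- Rate 5.6% in both groups, margin 2.52 points, one-sided 2.5% level, 85% power, 1,500 evaluable per group (section 12.1.1.2).
- 1,650 test subjects and about 1,643 controls in the propensity model (section 12.1.1.2).
- Bleeding: 2.19% v 4%, 1,650 v 1,240 subjects, 80% unadjusted power (section 12.1.2.2).

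**The plan's own sample size.** n = (1.960 + 1.036)² × 2 × 0.056 × 0.944 / 0.0252² = 1,495 per group, which agrees with the stated 1,500. Power at 1,500 per group is 85.1%.

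**Ratio of the two definitions.** With S = Σ var_i, the words give √(S/5) and the formula gives √(S/25). The ratio is √(25/5) = √5 = 2.236, whatever the rates or quintile sizes.

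**Which one is right.** The variance of a mean of five independent estimates is S/25, so the formula is correct. With equal quintiles the words reduce to √var_i, the standard error of one quintile alone, as if averaging five gained no precision.

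**Size, balanced quintiles (330 v 328.6 each, 5.6% throughout)**

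- var_i = 0.056 × 0.944 × (1/330 + 1/328.6) = 0.00032107
- Formula: √(5 × 0.00032107/25) = 0.00801
- Words: √0.00032107 = 0.01792

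The true sampling SD of d̄ is 0.00801 whichever SE is programmed. Power is therefore Φ((0.0252 − 1.96 × SE used)/0.00801).

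| | Formula | Words |
|---|---|---|
| SE (points) | 0.80 | 1.79 |
| 1.96 × SE (points) | 1.57 | 3.51 |
| Largest d̄ that passes (points) | +0.95 | −0.99 |
| Power | 88.2% | 10.8% |
| Coverage of the nominal 97.5% upper bound | 97.5% | Φ(1.96 × √5) = 99.9994% |

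A binomial simulation (200,000 runs, 330 v 329 per quintile) gave an SD of d̄ of 0.00800, power of 88.2% v 11.1%, and coverage of 97.50% v 99.998%.

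**Size, unbalanced quintiles.** The plan gives no split, so this one is assumed: the quintiles hold 8%, 14%, 20%, 26% and 32% of test subjects (132, 231, 330, 429, 528), with controls filling each quintile to 658.6.

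| | Formula | Words |
|---|---|---|
| SE (points) | 0.90 | 2.02 |
| 1.96 × SE (points) | 1.77 | 3.95 |
| Power | 79.8% | 5.6% |

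**Bleeding.** The pooled chi-square calculation gives 80.1%, agreeing with the stated 80%. With the unpooled SE, √(0.0219 × 0.9781/1,650 + 0.04 × 0.96/1,240) = 0.00663, unadjusted power is 77.9%. With that SE multiplied by √5 it is 4.9%.

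**Does the 85% power show which definition was intended?** It does not. The Synopsis says "The unadjusted comparison requires a minimum of 1,500 evaluable subjects per group", so that figure does not involve quintiles. At 1,500 per group the formula gives 85.1% with balanced quintiles and 76.1% with the assumed unbalanced split. This is a plausibility check only and no criticism of the sample size.

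**The case against.** The strongest reply is that the plan settles the matter where it arises. The full formula follows at once, both decision rules name SE(d̄), and no test procedure relies on the sentence. To go wrong, a programmer would have to ignore the displayed formula. On this view the sentence is a loose introduction, and the power figures describe an analysis nobody has planned.

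Most of that stands. The planned tests are valid, the figures apply only if the clause is used, and the unbalanced split is an assumption. Whether a separate SAP repeats the clause is unknown.

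A second reply is that SE(d̄) can be obtained from the mean variance by a further division by √5, so the sentence is only elliptical. That does not rescue it: the step is not stated, and the same paragraph uses the word mean in its ordinary sense for the point estimates.

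One limit should be kept in view. The error is conservative for the two endpoint tests, but not for everything. Section 12.3 compares quintile-adjusted baseline variables by normal approximation without saying which SE applies. An inflated SE there would make residual imbalance harder to see.

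**Conclusion.** The concern holds. One clause in section 12.1.1.3 gives a standard error exactly √5 = 2.236 times the one in the formula beside it. The formula is the correct one, with quintiles treated as independent, and it is the one the decision rules cite.

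The effect is nil if the formula is programmed. If the clause were programmed, death/MI power would fall from about 88% to 11% with balanced quintiles, or from about 80% to 6% under the assumed imbalance. These figures assume 5.6% in every quintile of both groups and 1,650 v 1,643 subjects. In both cases the half-width exceeds the 2.52-point margin. The risk for the endpoint tests is a false failure, not a false claim.

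This is a wording error and should be fixed, because a pre-specified co-primary test should carry only one definition of its standard error.

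**What to change.** In section 12.1.1.3, replace the clause with: *the adjusted standard error is SE(d̄) as defined below, i.e. one-fifth of the square root of the sum of the five quintile variances.*

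Check any separate SAP for the same clause and make the same edit there.

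The cost is one clause and that check. The formula, the decision rule, the margin, the sample size and section 12.1.2.3 need no change.

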### **8.1. Scale and Duration**

The EVOLVE Short DAPT Study will be conducted at up to 120 sites worldwide in the United States, Europe, Japan, and Brazil with planned enrollment of up to 2,250 subjects. Follow-up will be required at the following time points: 3 months, 6 months, 12 months and 15 months.

A schematic of the EVOLVE Short DAPT Study is shown on the following page in Figure 8.1-1.

[figure not shown]

Figure 8.1-1: EVOLVE Short DAPT Study

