### 12.1.2.3. Statistical Methods

The second propensity score model with quintile adjustment will be used to address baseline imbalance between the test group and the historical control group. The null hypothesis will be tested against alternative hypothesis using the propensity score quintile adjusted secondary endpoint of bleeding for testing superiority between the test group and the historical control group.

The adjusted between-group difference estimate ( $\bar{d}$ ) and the standard error ( $SE(\bar{d})$ ) of the adjusted between-group difference will be used to construct the 97.5% upper confidence bound of the adjusted between-group difference using normal approximation to binomial. If the 97.5% upper confidence bound is less than zero, the null hypothesis will be rejected for the secondary endpoint of bleeding and the test group will be concluded to be superior to historical control group.

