### **12.2.3. Number of Subjects per Investigative Site**

The maximum number of subjects to be enrolled per site is 200.

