#### **12.3.4. Justification of Pooling**

An assessment of the poolability of 3-month eligible subjects across sites will be performed based on:

- 1) the co-primary endpoint of all death/MI for the test group,
- 2) the co-primary endpoint of all death/MI for the control group,
- 3) the co-primary endpoint of ARC ST for the test group,
- 4) the secondary endpoint of bleeding for the test group, and
- 5) the secondary endpoint of bleeding for the control group

using logistic regression with site as a factor and co-primary endpoints as the outcome. Sites with fewer than 10 subjects enrolled will be combined into “virtual sites” based on geographic regions within United States, Europe, Japan, and Brazil, so that “virtual sites” have at least 10 subjects but no more than the largest enrolling site. If the two-sided P value for the site effect is  $\geq 0.15$ , it will be concluded that the site effect is not different across sites, and the site data can be pooled. If the two-sided P value for site effect is  $<0.15$ , site differences will be explored.

The poolability assessment of the treatment-by-site interaction based on the common sites enrolling both the 3-month eligible test subjects and the historical control subjects will be performed:

- 1) the co-primary endpoint of all death/MI for the 3-month eligible test/control subjects and
- 2) the secondary endpoint of bleeding the 3-month eligible test/control subjects.

An assessment of the poolability of subjects across sites will be made using logistic regression with treatment, site and the interaction of site by treatment as independent variables and co-primary endpoints as the outcome. The same model will be assessed for the secondary endpoint as the outcome. Sites with fewer than 10 subjects enrolled will be combined into “virtual sites” based on geographic regions within United States, Europe, Japan, and Brazil, so that “virtual sites” have at least 10 subjects but no more than the largest enrolling site. If the two-sided P value for the interaction coefficient is  $\geq 0.15$ , it will be concluded that the treatment effect is not different across sites, and the data can be pooled. If the two-sided P value for the interaction coefficient is  $<0.15$ , site differences will be explored.

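### The death/MI bound treats subjects as independent; if event rates vary between sites beyond the covariates it is too narrow, by an amount that the documents do not let one fix

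*Combined protocol and SAP*

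**What the plan says.** - **The bound (12.1.1.3).** The adjusted difference d̄ is the plain mean of five quintile differences, with Var(d̄) = (1/25) Σ var(d_i). These "will be used to construct the 97.5% upper confidence bound of the adjusted between-group difference using normal approximation to binomial (z-test". There is no site term and no covariance between quintiles. The only geographic covariate in Table 12.1-1 is US against outside US. The prose before the formula describes a different standard error: the root of the average of the five variances.
- **Bleeding (12.1.2.3).** The same quantities "will be used to construct the 97.5% upper confidence bound of the adjusted between-group difference using normal approximation to binomial".
- **Sites.** The study "will be conducted at up to 120 sites worldwide" (8.1), and 12.2.3 sets a cap: "The maximum number of subjects to be enrolled per site is 200". Controls come from three earlier studies; the number of their sites is not given.
- **Site tests (12.3.4).** Site is tested within each group. Treatment-by-site is tested at the "common sites enrolling both the 3-month eligible test subjects and the historical control subjects". Both tests use a two-sided threshold of 0.15. Below it, "site differences will be explored"; nothing is said about changing the bound.
- **Sample size (12.1.1.2).** "With one-sided 2.5% significance level, the study will require a minimum of 1,500 evaluable subjects per group to provide 85% power". This is a calculation for independent subjects. The 10% added to the test group is for variability of the propensity model, not for clustering.

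**The concern.** In a trial randomised within site, site effects largely cancel from the group difference. Here treatment is fixed by study. A site that supplies only test subjects or only controls passes its whole effect into d̄. Two independence assumptions then matter: the binomial variance within each quintile, and the zero covariance between quintiles, although one site may supply subjects to several quintiles and so make the d_i correlated.

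If sites differ beyond the covariates, the planned standard error is too small. At a true excess equal to the margin, non-inferiority would be declared more often than 2.5% of the time, on one of two endpoints that must both be met. The stated power would also be too high.

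**Working it through.** **1. The plan's own figure.** Inputs from 12.1.1.2: "The expected rate of 5.6% for 3 to 15 month death/MI rates in subjects at high risk for bleeding for both test and control groups", margin 2.52 points, one-sided 2.5%, 85% power. The normal-approximation formula gives 1,495 per group against the stated 1,500, and power at 1,500 per group is 85.1%. The design figure reproduces, for independent subjects.

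At the numbers to be analysed (1,650 test, 1,643 control), SE = √[0.056 × 0.944 × (1/1,650 + 1/1,643)] = 0.00801, and power = Φ(0.0252/0.00801 − 1.96) = 88.2%.

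**2. Assumptions not in the documents.** ICC from 0 to 0.02; 120 control sites, to match the maximum of 120 test sites; no shared sites; site-size coefficient of variation (CV) 0, 0.8 or 1.2. Mean evaluable subjects per site: m = 1,650/120 = 13.75, used for both groups.

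The between-site SD implied at a 5.6% rate is √(ICC × 0.056 × 0.944): about 1.0, 1.6, 2.3 and 3.3 points at ICC 0.002, 0.005, 0.01 and 0.02.

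**3. Error of the planned bound.** Design effect DE = 1 + [m(1 + CV²) − 1] × ICC; actual one-sided error = 1 − Φ(1.96/√DE). Example, CV 0.8 and ICC 0.01: DE = 1 + (13.75 × 1.64 − 1) × 0.01 = 1.216, √DE = 1.102, error 3.8%.

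| ICC | CV 0 | CV 0.8 | CV 1.2 |
|---|---|---|---|
| 0 | 2.5% | 2.5% | 2.5% |
| 0.002 | 2.65% | 2.75% | 2.9% |
| 0.005 | 2.9% | 3.1% | 3.5% |
| 0.01 | 3.25% | 3.8% | 4.4% |
| 0.02 | 4.0% | 5.1% | 6.4% |

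**4. Check by simulation.** The five-quintile estimator was simulated at the null boundary (8.12% v 5.6%) with beta-distributed site risks, 6,000 runs per setting and Monte Carlo error of about 0.2 to 0.3 points. With disjoint sites, error was 3.9% at ICC 0.01 and 4.9% at 0.02 (CV 0.8), and 6.8% at ICC 0.02 (CV 1.2). With half the sites common to both groups, error at ICC 0.02 and CV 0.8 fell from 4.9% to 3.7%. At ICC 0.01 and below, half-shared and disjoint sites showed no consistent difference beyond simulation noise.

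**5. Power with a valid standard error.** Inflating 0.00801 by √DE at CV 0.8 gives 84.8%, 81.4% and 74.8% at ICC 0.005, 0.01 and 0.02. The plan states 85%.

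**6. The two standard errors in 12.1.1.3.** In words: √[(1/5) Σ var_i]. By formula: √[(1/25) Σ var_i]. The ratio is √5 = 2.24. The verbal version gives SE = 0.0179 and power Φ(0.0252/0.0179 − 1.96), about 29%, which cannot be squared with the 85%. The largest clustering inflation above is √1.651 = 1.285, so the verbal SE would not be too small in any setting shown. This point therefore applies to the formula.

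**The case against.** - **Site overlap.** A reader might infer that test and control sites are largely different. The documents do not say so. Section 12.3.4 plans an interaction test at common sites for both death/MI and bleeding, so overlap was expected. Its extent is not given, and the figures in the table assume none. Where a site supplies both groups, its effect partly cancels and the error can even run the other way.
- **Site size.** A reader might take sites of 200 as the planned case. That is a cap on enrolment. After the planned losses it is 200 × 0.85 × 0.97 ≈ 165 evaluable; ten such sites per group would give 7.3% error at ICC 0.005. The average with 120 sites is about 14, and that average, with the spread of site sizes, drives the table.
- **No ICC.** None is documented, and no part of the range used can be called more likely from these documents. The covariate list is long and may absorb much of the site variation. Section 8.3 asserts little residual variation, but between trials, not sites. The study-level death/MI counts in the synopsis (13/253, 14/318, 11/85, that is 5.1%, 4.4% and 12.9%) are uneven, but they are crude and also not about sites.
- **Power.** The loss should be counted from the stated 85%, not from 88%. At ICC 0.005 and CV 0.8 the extra subjects absorb it, although the plan reserves those in the test group for model variability.
- **Site is not ignored.** Section 12.3.4 tests it at a lenient level, and 12.2.2 allows sensitivity analyses. Neither changes the bound that decides the endpoint.

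The size of the problem is therefore open. The direction, wherever one-group sites predominate and site variation remains, is not.

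**Conclusion.** The point holds in conditional form. The formula in 12.1.1.3, and the same bound in 12.1.2.3, make no allowance for site in a design where site effects cancel only at shared sites. The planned site tests do not repair this.

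Under disjoint sites and about 14 evaluable subjects per site, the excess over 2.5% is below half a point at ICC 0.002, up to about 1 point at 0.005, about 0.8 to 1.9 points at 0.01 and 1.5 to 3.9 points at 0.02. Power against the stated 85% is essentially unchanged at ICC 0.005 (CV 0.8), and falls by about 4 points at 0.01 and 10 points at 0.02. Shared sites reduce these figures.

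A reader might conclude that false non-inferiority is known to exceed 2.5%. The documents do not support that, because ICC, control site count and overlap are all unstated. It is worth changing because the correction is cheap and a choice made after the results are seen would carry little weight.

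**What to change.** First, make the words and the formula for the standard error in 12.1.1.3 agree.

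Then, in 12.1.1.3 and 12.1.2.3, keep d̄, the margin (zero for bleeding) and the decision rule, but compute SE(d̄) by site:

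- Each subject contributes ±(1/5)(y − p_ig)/n_ig, plus for test and minus for control, where p_ig and n_ig are the event rate and number in that quintile and group.
- Sum these over all five quintiles within each site to give U_s. A site that supplied both groups is one cluster.
- With S sites, Var(d̄) = [S/(S − 1)] Σ U_s². A bootstrap that resamples whole sites is an alternative.

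Use this SE for the 97.5% upper bound and report the binomial SE alongside. State in 12.1.1.2 and 12.1.2.2 that the 85% and 80% powers assume independent subjects.

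**Cost.** Analysis-plan wording and a few lines of code, before the analyses are run, as 12.3.7 allows. Site identifiers for both groups are already needed for 12.3.4. No subjects or data are added. With no clustering almost nothing changes (simulated SE 0.00799 v 0.00802 at ICC 0). With clustering the bound is somewhat wider and effective power lower: at ICC 0.02, 120 sites per group and CV 1, the true SD of d̄ was 0.0100, the planned SE averaged 0.0080 and the clustered SE 0.0098. The clustered SE is not exact; its simulated error ran from about 2.3% to 3.7% across the settings tried.
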